To assess the impact of the *Aalana Palana* intervention, we propose a quasi-experimental, non-randomized post-test only design incorporating a convenience-based comparison group. The study will be conducted in the catchment areas of 30 Anganwadi Centres (AWCs), previously identified as implementation sites through partnerships with government and community stakeholders.

Household mapping within these catchment areas will be undertaken to identify eligible participants, specifically caregivers of children under three years of age. All eligible participants who provide informed consent will be included in the study. The intervention (or “exposed”) group will comprise caregivers who report having viewed an *Aalana Palana* video within the three months preceding data collection.

A comparison (unexposed) group will be formed using a convenience sampling approach, including participants from the same catchment areas who have not been exposed to the intervention. Importantly, participation in the study will not be restricted to households registered at an AWC, allowing for the inclusion of a broader range of community members and enhancing the generalizability of findings within the selected geographies.

This design enables the assessment of real-world exposure and its potential effects under naturalistic conditions while acknowledging limitations related to non-random allocation.

Data Collection Tools

For all participants who consent to participate in the proposed study, basic demographic and identifying information will be collected, including GPS coordinates of households; child’s name, sex, and date of birth; names and dates of birth of parents; contact details; address; and maternal education level. Maternal education will be categorized using classifications from the modified Kuppuswamy scale (25), which has been adapted for Indian socio-economic contexts.

Assessment of Exposure to Aalana Palana

Exposure to the *Aalana Palana* intervention will be determined through a structured set of questions developed by the intervention team. These will include:

- (i) Whether the participant has heard of *Aalana Palana* (with follow-up on the source of information);
- (ii) Whether the participant has watched any *Aalana Palana* video in the three months prior to data collection;
- (iii) Whether anyone in the household has any *Aalana Palana* video stored on their mobile device (with follow-up on the source).

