Two different teams were deployed to collect data between July 2023 and January 2024. This was done to minimize assessor bias by ensuring that exposure and outcome data was collected by two separate teams. The first team comprised of two field workers who mapped the study geography, consented eligible participants, and collected data on geolocations, demographic, socio-economic, and exposure to *Aalana Palana*. The list of consented participants identified by the first team was shared with a second team who visited the households three-to-four weeks post consenting. The second team of non-specialist child development assessors collected all outcome data on FCI, CREDI, and IYCF practices. Data on IYCF practices was collected from a subset of children aged >6 months and <2 years at the time of data collection.

Data Analysis

All data will be analyzed using Stata 15 and SPSS 27.

- Descriptive Analysis: Frequencies, means, and standard deviations will be used to summarize participant characteristics, exposure levels, and outcomes. Group differences will be tested using chi-square tests for categorical variables and t-tests for continuous variables.
- Primary Analysis: Linear regression will be used to estimate the association between intervention exposure and CREDI z-scores, adjusting for child age, child sex, maternal education, FCI score, and AWC registration status.
- Secondary Analyses:
 - Logistic regression will assess the association between exposure and binary outcomes for FCI and MAD.
 - Moderation analysis will examine interaction effects of child age, sex, and maternal education on the primary outcome.

- Mediation analysis will be conducted using structural equation modeling (SEM) to assess whether the effect of the intervention on child development is mediated by the quality of the home environment (FCI score).

Sensitivity Analysis: Subgroup analyses will be performed for caregivers registered at AWCs to account for potential confounding due to engagement with AWC services.

Data Management and Confidentiality

Data will be collected digitally on secure tablets using encrypted platforms (e.g., REDCap). Data will be uploaded to a password-protected server accessible only to designated research personnel. Identifiers will be stored separately from de-identified datasets. Regular backups and integrity checks will ensure data security and accuracy.

Ethics Approval and Consent

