Ethical approval has been granted by the Sangath Institutional Review Board (Ref: RR_2019_58). Written informed consent will be obtained in the local language (Telugu) from all participants. Illiterate participants will consent via witnessed thumbprint. All field staff will be trained in ethical research practices, confidentiality, and participant rights.

Limitations

This quasi-experimental study may be affected by confounding and selection bias due to the absence of randomization. We will address this through multivariable regression, and subgroup analyses. Lack of baseline data and reliance on caregiver recall are additional limitations. However, use of standardized tools and blinded outcome assessors mitigate potential bias.

References

2. Nurturing care framework progress report 2018-2023: reflections and looking forward [Internet]. [cited 2025 May 11]. Available from: <https://www.who.int/publications/i/item/9789240074460>

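### Socio-economic data are said to be collected, but maternal education is the only socio-economic covariate in the primary CREDI model, so residual socio-economic confounding is plausible and its size cannot be judged

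*Combined protocol and SAP*

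**What the plan says.** All references are to the combined protocol and SAP.

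- **Design (Study Design and Participants).** The study is a "non-randomized post-test only design incorporating a convenience-based comparison group". The exposed are "caregivers who report having viewed an" Aalana Palana video in the previous three months. For the others, "A comparison (unexposed) group will be formed using a convenience sampling approach", drawn from the same catchments.
- **Data recorded (Data collection).** The first team "collected data on geolocations, demographic, socio-economic, and exposure to" the intervention. A second team returned three to four weeks after consent for FCI, CREDI and feeding outcomes.
- **Items named (Data Collection Tools).** Besides household GPS position and the child's name, sex and date of birth, the list gives "names and dates of birth of parents; contact details; address; and maternal education level". The modified Kuppuswamy scale is used only to classify maternal education.
- **Primary model (Data Analysis).** Linear regression of CREDI z-scores on exposure, "adjusting for child age, child sex, maternal education, FCI score, and AWC registration status". The logistic models for FCI and MAD state no covariates.
- **Handling of confounding (Limitations).** Confounding and selection bias are acknowledged: "We will address this through multivariable regression, and subgroup analyses". No matching, weighting or propensity method is planned.

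**The concern.** Who views a video is not random. It depends on contact with the Anganwadi worker and, for the short clips, on someone sharing them. Both may track household circumstances, which may also affect child development, play materials and diet. The protocol's introduction itself links developmental risk to social and structural inequity. Households not registered at an AWC are admitted, which may widen the range of circumstances.

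With no randomization and no baseline, the exposure coefficient can be read as an effect only as far as the covariates capture these differences. Following the listed covariates would leave out any recorded socio-economic measure other than maternal education, and parental age as well. The direction of any resulting bias is not predictable: users of AWC services may be poorer than their neighbours, while caregivers reached by phone may be better off.

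**Working it through.** The plan gives no sample size, SD, expected effect or standard error, so there is no figure to reproduce. The check compares what is recorded with what is adjusted for, then shows what a gap could be worth under stated assumptions.

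**1. Recorded against modelled**

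| Variable | Recorded? | In primary model? |
|---|---|---|
| Child age, child sex | Yes, itemised | Yes |
| Maternal education | Yes, itemised | Yes |
| AWC registration | Not itemised, but used | Yes |
| FCI score | Yes, at the outcome visit | Yes |
| Parents' dates of birth | Yes, itemised | No |
| Other socio-economic items | Category named, items not listed | No |

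The itemised list opens with a word that marks it as partial, and AWC registration is used without appearing in it. The list is therefore not complete. Further socio-economic items are possible but not shown.

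**2. Whether another model term fills the gap**

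- AWC registration is described at household level and captures contact with the service. It does not measure means.
- FCI is collected after exposure, and the mediation analysis places it on the path from intervention to development. It is not a background measure of circumstances.
- The registered-only analysis is aimed at engagement with AWC services. Viewers and non-viewers within that subgroup can still differ in circumstances.
- The descriptive group tests could reveal an imbalance, but nothing in the plan carries it into the model.

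**3. Possible size (both inputs assumed)**

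For a linear model, bias = g × d. Here g is the CREDI difference, in SD, per SD of the omitted measure, and d is the exposed-minus-unexposed difference in that measure, in SD. Both are conditional on every covariate in the model.

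- g and d each 0.1 to 0.3: 0.1 × 0.1 = 0.01 SD up to 0.3 × 0.3 = 0.09 SD.
- g 0.05 to 0.20 and d 0.1 to 0.5: 0.05 × 0.1 = 0.005 SD up to 0.20 × 0.5 = 0.10 SD.

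The bias takes the sign of g × d, so it can go either way. Because the listed model includes FCI, which covers play materials, g may lie toward the low end.

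**4. What such a bias would do to a test**

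Assume a true null, n per group, unit SD, independent observations and SE = √(2/n). A two-sided 5% test then rejects with probability 1 − Φ(1.96 − bias/SE) + Φ(−1.96 − bias/SE).

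| Bias (SD) | n = 100 | n = 200 | n = 400 |
|---|---|---|---|
| 0.02 | 5.2% | 5.5% | 5.9% |
| 0.06 | 7.1% | 9.2% | 13.6% |
| 0.10 | 10.9% | 17.0% | 29.3% |

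For example, at n = 200, SE = √(2/200) = 0.10. A bias of 0.10 is then one standard error, and the rejection rate is 17.0%. The sample sizes are illustrations only. A larger sample does not remove the bias.

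**The case against.** The strongest reply is that the data may not exist. The only socio-economic item named is maternal education, and the word socio-economic in the Data collection section may mean no more than that. This stands: a reader might infer that the bias is avoidable with data in hand, and for socio-economic position the documents do not establish it. For parental age they do, since dates of birth are itemised. The documents make no specific case for maternal age as a confounder, however, so that addition rests on general plausibility.

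Other tempting readings also go too far:

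- *That maternal education is the only household characteristic adjusted for, or that no other recorded demographic data are used.* AWC registration is also a household-level term, and child age and sex come from the recorded demographic data.
- *That viewing requires the caregiver's own phone.* Study Setting reports personal phone use by 60% of women, but also household ownership of 96% (urban) and 91% (rural). Videos were loaded on the workers' phones and used mainly in group sessions. Phone access matters chiefly for the shared clips.
- *That the comparison group selected itself.* It is a convenience sample; the self-selection lies in who viewed.
- *That a null or positive result would be an artefact.* Without a sample size or standard error, this cannot be said.

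It is also fair that the plan discloses confounding and already tests group differences descriptively. Disclosure does not make the covariate list adequate, and the planned tests do not alter the model.

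**Conclusion.** The point holds in limited form. Adjustment is the main defence against confounding, and a category of data described as socio-economic is collected before the outcomes. The fixed covariate list nevertheless has maternal education as its only socio-economic term and omits parental age. This is more than missing detail, because following the list leaves recorded potential confounders out of the primary model.

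Residual socio-economic confounding is plausible but not demonstrated. The range of about 0.01 to 0.09 SD, in either direction, is wholly assumed. Its lower end is negligible; its upper end could matter for a test. The documents cannot settle which applies. The change should be made because it is cheap and lets the data answer the question, not because a material bias has been shown.

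**What to change.** 1. List the socio-economic items that the first team recorded.
2. Add those items, and mother's age from her date of birth, to the primary CREDI model alongside child age, child sex, maternal education and AWC registration. State the same background covariates for the FCI and MAD logistic models.
3. Report exposed-unexposed balance on these variables beside the adjusted estimates.
4. If maternal education is the only socio-economic item, add mother's age and state under Limitations that household socio-economic position is uncontrolled.
5. Data collection ended in January 2024 and the document is dated 14 May 2025. Date the change, label it as made after data collection, and also report the model with the covariates listed in the current plan.

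Whether FCI belongs in the primary model is a separate question that changes what is estimated. This change should neither settle it nor drop FCI without saying so.

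Cost: no new data and probably a few degrees of freedom, though the exact number depends on the unlisted items. The real downside is a covariate set changed after data collection, which is why both models should be shown.

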Given these challenges, the study will build on existing collaborations between Sangath, UNICEF, and the Department of Women Development and Child Welfare (DWDCW), Government of Telangana. The intervention, *Aalana Palana*, is proposed to be implemented within the Integrated Child Development Services (ICDS) framework (15). This initiative would be delivered across 30 Anganwadi Centres (AWCs) spanning three ICDS projects: Maheshwaram, Khairtabad, and Alwal. AWCs serve as key community-level service delivery points, catering to approximately 5,000 people in urban and 1,000 in rural areas, and are managed by Anganwadi Workers (AWWs), a cadre of community-based frontline workers.

A key enabling factor for intervention delivery in this context is the widespread mobile phone access in Telangana, with 96% of urban and 91% of rural households owning a mobile phone. Furthermore, 60% of women in the state have access to a mobile phone that they use personally, which enhances the feasibility of integrating digital or hybrid models of ECD delivery (14).

This context provides a strong foundation to evaluate and scale integrated, community-based, and technology-supported ECD interventions within public systems like the ICDS in Telangana.

The Aalana Palana Intervention

Aalana Palana is a facilitated video-viewing intervention combining responsive parenting and nutrition messaging. *Aalana Palana* which, in the local language Telugu, translates to ‘caring and nurturing’, represents a transition from largely paper-based counselling sessions to a facilitated video viewing, discussion and demonstration model. It aims to ensure fidelity of the intervention delivery by standardising the content delivered during sessions. AWWs would use these videos to conduct both individual and group counselling sessions with caregivers at AWCs and family homes. *Aalana Palana* was developed using the following steps:

Development of video content

Information synthesis: A desk review of published global research on parenting interventions specifically in LMICs, the Nurturing Care Framework (16), the WHO Care for Development Package (17), and the early years learning framework. Resources in the Indian context, such as the Mother and Child Protection card (18), Home-Based Care for Young Child (HBYC) program guidelines, Poshan Abhiyan (19), and *Intintiki Anganwadi* (20), were also reviewed for content and implementation guidelines.

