Training plan: Consultations with DWDCW and UNICEF were conducted to develop a capacity building plan which would be integrated within the existing training schedules of AWWs. A three-day training of four hours was implemented that focused on experiential

learning and role plays. Training content included session plans, learning objectives for each session, and expected competencies required for the delivery of *Aalana Palana*. The topics covered - importance of the early years of life and responsive caregiving, objectives of *Aalana Palana*, intervention content, values of two-way communication, intervention delivery processes, and supportive supervision. *Aalana Palana* videos were also uploaded on the phones of the AWWs using external solid-state drives and they were trained to select age-specific videos for session delivery.

In December 2021, 30 AWWs from three ICDS projects, along with their supervisors and Child Development Project Officers (CDPOs), underwent in-person training. Pre and post-tests were done at the beginning and end of each training day to understand any changes in knowledge and obtain feedback about sessions from AWWs.

Session delivery: Qualitative research conducted during the formative stage of *Aalana Palana* highlighted challenges on time use and workload of AWWs (21). One of the mitigation strategies that emerged during further consultations with AWWs which could facilitate effective implementation of *Aalana Palana* was the prioritisation of group over individual counselling sessions. Evidence also indicated benefits of parenting interventions involving group-based sessions on child outcomes, particularly in LMICs (24). Based on this, AWWs were encouraged to use the *Aalana Palana* videos primarily during group-based counselling sessions. AWWs started delivering *Aalana Palana* sessions from January, 2022.

Supportive supervision: The *Aalana Palana* team conducted at least one in-person supervision visit per month for all 30 AWWs and used a semi-structured questionnaire to observe the sessions. To record session delivery, stickers were placed next to the names of caregivers in existing registers maintained by AWWs.

The process of *Aalana Palana* video development and implementation can be seen in Figure 1.

[figure not shown]

Figure 1: Process of Aalana Palana video development and implementation

Study Design and Participants

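### The analysis plan states no allowance for clustering by Anganwadi Centre (AWC), so the primary standard error is too small if exposure and residual outcome both cluster positively by centre

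*Combined protocol and SAP*

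**What the plan says.** All of this is in the combined protocol and SAP.

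- **Data Analysis, Primary Analysis:** "Linear regression will be used to estimate the association between intervention exposure and CREDI z-scores". The adjustment set is the child's age and sex, the mother's education, the FCI score and whether the household is registered at an AWC.
- **Data Analysis, other analyses:** logistic regression for FCI and MAD, moderation by age, sex and maternal education, SEM mediation, and a subgroup analysis of registered caregivers. No centre effect, multilevel model or clustered variance is named for any of them. On software: "All data will be analyzed using Stata 15 and SPSS 27".
- **Study Design and Participants:** "The study will be conducted in the catchment areas of 30 Anganwadi Centres (AWCs". The comparison group is formed by "including participants from the same catchment areas who have not been exposed to the intervention".
- **Implementation, Training plan and Session delivery:** those trained were "30 AWWs from three ICDS projects, along with their supervisors", and they were encouraged to use the "videos primarily during group-based counselling sessions".
- **Study Setting:** AWCs are described as "catering to approximately 5,000 people in urban and 1,000 in rural areas", so catchments may differ in size.
- **Data collection:** "Two different teams were deployed to collect data between July 2023 and January 2024".

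Limitations names confounding, selection, the lack of a baseline and recall. It does not mention clustering.

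**The concern.** Ordinary regression errors treat every caregiver as independent. Here there are grounds to doubt that. Thirty workers were trained for 30 centres, and group sessions are the preferred mode. Exposure means having watched any video in the past three months, so how active a centre is could move many caregivers' exposure together. Children in one catchment may also resemble each other beyond what the covariates explain.

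Registration status does not appear to repair this. Households need not be registered to take part, so the variable seems to record whether a caregiver is registered, not at which of the 30 centres.

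At stake is the precision claimed for the primary effect: an interval that is too narrow and a test that rejects too often. The bias of the estimate is a separate matter.

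**Working it through.** **Inputs.** From the document: 30 centres, exposure recorded per caregiver, and both groups drawn from the same catchments. Not in the document, so assumed: a two-sided 5% test, m = 10, 20 or 40 children per AWC (n = 300, 600 or 1,200), residual outcome ICC (ICCy) 0.02, 0.05 or 0.10, and exposure ICC (ICCx) 0, 0.1, 0.3 or 0.5. The plan gives no sample size, power or design effect to reproduce.

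**Formula.** For a regression coefficient with equal centres:

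- true variance / ordinary variance: D = 1 + (m − 1) × ICCx × ICCy
- true SE / ordinary SE = √D
- actual type I error = 2 × [1 − Φ(1.96/√D)]

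| m | ICCx | ICCy | D | SE ratio | Type I error |
|---|---|---|---|---|---|
| any | 0 | any | 1 | 1.000 | 5.0% |
| 20 | 0.1 | 0.05 | 1 + 19×0.005 = 1.095 | 1.046 | 6.1% |
| 20 | 0.3 | 0.05 | 1 + 19×0.015 = 1.285 | 1.134 | 8.4% |
| 20 | 0.3 | 0.10 | 1 + 19×0.03 = 1.570 | 1.253 | 11.8% |
| 40 | 0.3 | 0.10 | 1 + 39×0.03 = 2.170 | 1.473 | 18.3% |
| 40 | 0.5 | 0.10 | 1 + 39×0.05 = 2.950 | 1.718 | 25.4% |

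Over the 27 unweighted cells with ICCx up to 0.3, type I error is 5.0% to 18.3%, median 5.9%, and three cells exceed 10%. Adding ICCx = 0.5 makes 36 cells: the median becomes 6.5% and eight cells exceed 10%, five of them at ICCx = 0.5.

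**Balanced exposure.** If every centre had the same exposed share, ICCx = −1/(m − 1) and D = 1 − ICCy. For ICCy 0.01 to 0.10, D is 0.99 to 0.90 and the test rejects 4.9% to 3.9%, which is slightly conservative.

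**Which correction works.** Null simulation: 3,000 runs (Monte Carlo SE about 0.4 points), n = 600, no covariates. Centres are unequal (20 of 8 children and 10 of 44: 160 + 440 = 600). Rejection rates are in %; CR1 is the plain clustered error on t(29), CR2 is the bias-reduced version with Satterthwaite df, and the last column is a wild cluster bootstrap.

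| Exposed | ICCx | ICCy | Ordinary | CR1 | CR2 | Bootstrap |
|---|---|---|---|---|---|---|
| 50% | 0.17 | 0.05 | 7.7 | 6.0 | 4.7 | 4.9 |
| 50% | 0.17 | 0.10 | 10.6 | 6.1 | 4.7 | 4.5 |
| 15% | 0.13 | 0.05 | 7.0 | 7.3 | 4.6 | 4.9 |
| 15% | 0.13 | 0.10 | 9.5 | 8.4 | 5.3 | 5.2 |
| 50% | 0 | 0.05 | 5.2 | 6.0 | 4.8 | 4.9 |

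The mean Satterthwaite df is about 16 (50% exposed) or 11 (15% exposed), not 29. CR1 is no better than the ordinary error in the third row and worse in the fifth.

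**Moderation.** For exposure by child sex, with the same unequal centres and no between-centre variation in slopes, two sets of runs gave 4.6% to 5.5% for ordinary errors and 5.3% to 7.3% for CR1. Ordinary errors show no inflation.

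**Within-centre estimates.** If self-selection acts purely within centres (assumed correlation 0.085, no true effect), pooled against fixed-effects bias is 0.119 v 0.134 SD at ICCx 0.11, 0.112 v 0.136 at 0.17 and 0.098 v 0.139 at 0.30. The ratios of 1.12, 1.21 and 1.42 match 1/(1 − ICCx).

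**The case against.** The plan names no variance estimator, so linear regression could be run with clustered errors. That is true. But nothing in the document says so, and run as written the ordinary errors would be used. The gap in specification stands.

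Exposure may hardly cluster. Home sessions, shared short clips, stored videos, unregistered households and unexposed caregivers from the same catchments all pull that way. This also stands, and it is why the conclusion is conditional.

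Three stronger readings are tempting, and the document does not support them:

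- **That the cluster-trial design effect applies.** With m = 20 and ICC 0.05 it would be 1 + 19 × 0.05 = 1.95, against 1.095 to 1.285 above. It presumes that whole centres are exposed or not, whereas exposure here can vary within a catchment.
- **That every planned model is inflated.** The interaction with child sex shows no inflation when slopes do not vary between centres. Nothing has been quantified for the logistic or SEM models.
- **That handling centre would deal with confounding.** Clustered errors leave the estimate unchanged. Centre effects do not remove self-selection within centres and can enlarge its bias. No passage shows that between-centre confounding exists.

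**Conclusion.** The omission is certain from the text. So is the conditional statement: if exposure and residual outcome both cluster positively by AWC, the ordinary standard error for the primary effect is too small. A reader might infer that the planned errors are definitely too small, or badly so. The document supports neither, because it gives no n, ICC or exposure rate by centre.

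Under the assumed inputs up to ICCx 0.3, the true SE is 1.00 to 1.47 times the ordinary one. Most of the range is mild, and the 25.4% figure is a corner case. This should be fixed because the correction is cheap and the size cannot be ruled out from the document.

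**What to change.** 1. Report the primary linear regression with AWC-clustered standard errors and a small-sample correction suited to about 30 possibly unequal centres, for example CR2 with Satterthwaite df or a wild cluster bootstrap.
2. Choose the method without reference to the exposure result. Data collection ended in January 2024 and the document is dated 14 May 2025, so estimates may already exist. If they do, report the corrected result beside them and say so.
3. Use the same approach for the main exposure effects in the FCI and MAD logistic models where a suitable correction is available.
4. Do not fall back on plain CR1 errors by default. Where no small-sample correction is available, report the model-based result and state clustering as a limitation. Availability in Stata 15 and SPSS 27 must be checked, above all for SEM.
5. Report the outcome and exposure ICCs, children per AWC and the exposure rate by AWC. A within-AWC estimate is optional, with its effect on selection bias stated.

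**Cost.** Analysis work only. If AWC was not recorded, it can be assigned from the catchment mapping or household GPS. In the simulation, CR2 intervals are 4% to 8% wider than ordinary ones when the correction was not needed, and 11% to 29% wider at ICCx 0.13 to 0.17.
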